We will recruit 8 blind subjects between the ages of 7 and 18 from the UPMC Eye Center patient population, the Wicab website, the established volunteer list of over 200 blind subjects from the Sensory Substitution Laboratory, the Clinical Trials Registry at the University of Pittsburgh and the patient population at the ophthalmology department at the UPMC Children's Hospital. Recruitment of normally sighted controls is not justified. We expect to screen 15 blind subjects to achieve our enrollment target. Based upon estimates from our preliminary data, this sample size should allow us to show differences between the naïve and BrainPort condition with a significance level of p<0.05 and a power of greater than 0.8.

We will attempt to enroll an equal number of males and females to the extent this is possible. We will attempt to enroll minority populations in our study.

Inclusion Criteria

Volunteer subjects enrolled and treated in this study must meet all of the following criteria:

- 1. Between the age of 7 and 18
- 2. Blind (documented visual acuity of light perception or worse) in both eyes from an eye care provider.
- 3. Able to read (or have read to him or her), understand and sign the Informed Consent and Assent form.
- 4. Able to understand the training and rehabilitation protocols involved in the study.
- 5. Willing to use the BrainPort device

Exclusion Criteria

Subjects will be excluded from the study if they meet any of the following criteria:

- 1. Current oral health problems as determined by the subject's history, and an examination of the oral cavity performed by a member of the study team. Subject is excluded if any of the following conditions are met:
 - a. A history of injury to the tongue resulting in impaired sensation or use of the tongue.
 - b. Visible open lesions, cold sores, abrasions, blisters, or rash on the tongue.
 - c. Oral surgery or dental work in the past 3 months or anticipated to occur for the duration of participation in the study (does not include routine dental health exams/cleanings).
 - d. Piercing on the tongue.
 - e. Performance better than 20/5000 on the FrACT acuity test (same visual criteria as FDA safety study).
- 2. Known neuropathies of tongue or skin tactile system.
- 3. Unwilling or unable to adhere to all study requirements, including completion of the training period, evaluation tests and follow up visits.
- 4. Implanted electrical medical devices such as pacemakers.

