Following consent, subjects will complete baseline psychophysical assessments which have been used in similar BrainPort studies. These consist of simple and easy to understand computer based tests of the ability to detect light, direction, motion, and letters. In addition, we may administer seated tests where the subject is asked to recognize objects, pictures or depth cues. Each of these tests takes between 5 and 15 minutes to complete.

Following baseline studies, a structured "Clinical Training Phase" with the will occur. Our lab has trained over 100 subjects to use the BrainPort device (largest center worldwide), and has established the methods to provide core skill acquisition under the direction of an occupational therapist who works in our laboratory (refer to attachment). Because the subjects in this study will not be taking the device home, but will be restricted to limited use in the controlled laboratory setting, the training will not have to involve outdoor navigation or more advanced skills. After the Brainport training phase has been completed, and the subject has demonstrated basic proficiency with the device, the same set of outcomes assessments administered at baseline will be repeated.

If at any point during the study, the subject subsequently does not meet inclusion criteria or satisfies exclusion criteria, or wishes to stop participation, further testing will be discontinued and the subject will be dismissed.

Detailed description of study design by visit:

Session 1:

- Informed consent
- Review of inclusion and exclusion criteria
- Baseline medical and medication history
- Oral exam
- Baseline psychophysical assessments

Session 2, 3, & 4:

- Training session
- Oral exam

Session 5:

- Repeat outcomes assessments with Brainport
- Oral exam

Each session is expected to last 90 minutes, will be performed at the UPMC, and will be performed by the Research Staff and/or PI.

Note: follow up visits can be combined into a single longer day with morning and afternoon sessions at the request of the subject. We are allowing this because subjects and their families are responsible for their own travel, lodging and meal expenses.

Evaluation Procedures/Outcomes Assessments (Detailed descriptions):

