Investigators will assess subjects for adverse events during each training session and each follow-up visit. Oral exams will be performed at baseline, and at the end of each session. Subjects will also be asked at each visit whether they have experienced any medical problems since their last visit and whether or not they would consider the problems to be due to the device use. All expected and unexpected untoward occurrences related to the Brainport will be considered adverse events and will be reported to the PI, and the reviewing IRB as soon as possible but no later than 10 days following the occurrence. Subjects will be instructed to report any suspected adverse event to the research staff immediately.

Potential adverse events that will be monitored for with the BrainPortTM vision device include the following:

- A mild tingling sensation or residual sensation in the region of the electrical stimulus on the tongue. While unusual, this sensation is not reported to be annoying, does not interfere with normal activities, and it fades with time.
- Discomfort associated with the electrical stimulus on the tongue. No observed or received reports of tongue irritation or pain occurred during a one year long FDA safety study in 75 subjects. Although no long-term adverse events are known or expected, no data is available on the long-term effects of electrical stimulation of the tongue.

Investigators will be asked to report and evaluate all adverse events and indicate the probable relationship to the device. All adverse events will be followed until they are resolved or the investigator has determined the condition to be chronic or stable or the subject's participation in the study has been terminated.

ETHICAL CONSIDERATIONS

Risks and Mitigation Strategies

There are no foreseeable risks involved in the proposed psychophysical and object recognition testing for visual function as these involve looking at a computer monitor or other objects while seated.

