It is possible that the stimulus on the tongue may seem too strong and produce discomfort. Subjects have complete control of the sensation strength, and can adjust it to their preference. However, they can also simply remove the electrical stimulator at any time or press a button to end the stimulus. Some subjects have reported a mild buzzing sensation on the tongue, lasting from several minutes for up to one hour, after the stimulus is turned off. While unusual, this sensation is not reported to be annoying and does not interfere with normal activities, such as taste, talking or swallowing. Subjects will be asked to report this sensation to the study staff. Additional known risks arising from use of the BrainPort[™] balance device are minor. These potential risks include a risk that the materials used in the construction of the device may irritate the mouth or tongue, irritation of the tongue from the electrodes on the component of the device that contacts your tongue, excessive electrical stimulation from the strength of the signal coming through the electrode array resulting in discomfort to the tongue, and the ongoing risks of falls. If the device becomes displaced in your mouth, there is a chance that you will bite down on it and injure your tooth/teeth There is a slight risk of electrical shock. These risks may be minimized through the assessment and education of study participants in the orientation phase of the study, instructions to limit the electrical stimulation and signal strength to a safe level, training subjects to set the electrical stimulation level according to their preferred level of strength, using only device materials that have been previously tested to be sure the materials of the device are suitable for contact with and use in the mouth and close guarding by the clinician during the Training Phase. Wicab, Inc. has not observed any significant adverse events during prior clinical studies of the BrainPortTM vision devices. Nor has the company observed adverse events during studies of a similar device used for balance rehabilitation. There also may be other side effects that are not known. Many side effects go away shortly after use of the BrainPort[™] is stopped, but in some cases side effects can be serious, long lasting, or may never go away. There is not enough medical information to know what the risks might be to a breast-fed infant or to an unborn child carried by a woman who takes part in this study. Therefore, a women who can become pregnant must state whether she is pregnant before taking part in this study. It is also important when using the device that subjects do not take any additional physical risks that they would not take ordinarily. Risks include injury due to bumping into objects or falling when walking with the device. Subjects will be closely monitored by the study staff and prevented from bumping objects whenever he or she is ambulatory.

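### Required adverse-event follow-up may stop when participation ends, and a device-related tongue lesion can itself end participation, so its outcome could go unrecorded

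*Combined protocol and SAP*

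**What the plan says.** Four parts of the protocol bear on this point.

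- **ADVERSE EVENTS, follow-up.** Follow-up has three alternative end points: resolution, an investigator's judgement that the condition is chronic or stable, "or the subject's participation in the study has been terminated".
- **ADVERSE EVENTS, detection and reporting.** "Oral exams will be performed at baseline, and at the end of each session". Events go to the PI and the IRB "as soon as possible but no later than 10 days following the occurrence", and investigators indicate the probable relationship to the device.
- **Overview of Study Design.** If at any point "the subject subsequently does not meet inclusion criteria or satisfies exclusion criteria", or the child wishes to stop, then "further testing will be discontinued and the subject will be dismissed".
- **Exclusion Criteria, item 1b.** "Visible open lesions, cold sores, abrasions, blisters, or rash on the tongue". The item makes no distinction by cause.

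Risks and Mitigation Strategies adds two statements. It names "irritation of the tongue from the electrodes on the component of the device that contacts your tongue" as a potential risk, in a passage introduced as concerning the BrainPort balance device. It also says of side effects in general that many fade soon after use stops, but "in some cases side effects can be serious, long lasting, or may never go away".

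**The concern.** Ending safety follow-up at study exit is a common limitation. Here the adverse event can itself cause the exit. The device stimulates the tongue, the oral exams look for tongue findings, and a visible lesion is an exclusion criterion that applies throughout the study. Followed literally, the rules allow follow-up to stop for the kind of finding the exams are there to catch. A child who leaves because of discomfort reaches the same end point by the withdrawal route.

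At stake is one item of safety information: whether a device-related lesion in a child healed. The section itself acknowledges that long-term effects of electrical stimulation of the tongue are unknown. No efficacy result is affected.

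**Working it through.** The plan gives no figure to reproduce. The check is to read the rules together and look for anything that closes the gap.

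**Step 1: is termination sufficient alone?** The three end points in ADVERSE EVENTS are joined by *or*. An event that is neither resolved nor stable therefore needs no further follow-up once participation is terminated.

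**Step 2: do the exclusion criteria apply after enrolment?** Yes. Overview of Study Design applies them at any point during the study.

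**Step 3: can a device-related finding meet one?** Item 1b lists open lesions, abrasions, blisters and rash, and exempts no cause. A device-related finding of that kind would qualify. Irritation without a visible lesion would not, nor would the tingling and discomfort that ADVERSE EVENTS lists for monitoring.

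**Step 4: does dismissal equal termination?** The protocol does not say so, but it is the natural reading. The chain rests on it.

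**Step 5: does anything else require later contact?**

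- The 10-day rule covers the report of the occurrence, not its outcome.
- Asking about medical problems at each visit requires that there be a next visit.
- ADVERSE EVENTS mentions follow-up visits, but the visit-by-visit description ends at Session 5.
- The meetings and record inspections under STUDY MONITORING review what has been collected and require no contact with a dismissed child.

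The number of contacts required after dismissal is therefore 0.

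**Step 6: planned exams after detection.** Oral exams are listed at Sessions 1 to 5, and device training starts at Session 2. Exams remaining after Session k = 5 − k:

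| Lesion found at Session | Planned exams remaining |
|---|---|
| 2 | 5 − 2 = 3 |
| 3 | 5 − 3 = 2 |
| 4 | 5 − 4 = 1 |
| 5 | 5 − 5 = 0 |

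These counts describe the schedule only. Study Duration allows two sessions a day, so five sessions can fit into three days (5 / 2 = 2.5, rounded up). The remaining exams could then fall within hours or a day or two of detection. Even the full schedule takes only about two weeks.

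**Step 7: Session 5.** If *terminated* includes normal completion, an event open at the last session needs no follow-up either. If it means early termination only, that event must be followed. The text does not settle this.

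**The case against.** The strongest reply is that the event is hypothetical. No passage says that the device causes an open lesion, abrasion, blister or rash. The irritation risk is listed under the balance device, and irritation alone does not meet item 1b. ADVERSE EVENTS reports no tongue irritation or pain in a one-year safety study of 75 subjects. Risks and Mitigation Strategies reports no significant adverse events in earlier studies of the vision device, and REGULATORY CONSIDERATIONS places the study under non-significant-risk rules. The warning about lasting side effects is general and does not refer to tongue lesions. All of this stands as evidence about likelihood. It does not change what the stopping rule permits if a lesion occurs.

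A second reply is that silent loss is unlikely. A parent or caregiver attends every visit, the event reaches the PI and the IRB, investigator meetings cover adverse events, and dismissal ends testing rather than care. Nothing prevents a clinician from following the child. This too stands, and it narrows the gap, but none of these safeguards requires the outcome to be recorded.

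A third reply is that the consent pages are not in the available file and may already provide for contact after withdrawal. That cannot be checked here. It is a reason to make the forms and the protocol agree, and it limits the point to what the protocol text requires.

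A reader might also infer from the cancelled exams that 3, 2 or 1 observations of healing are lost. The documents do not support that. With two sessions a day allowed, those exams might come too soon to show healing, so their number does not measure lost information.

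**Conclusion.** The point holds as a minor gap in the safety rules. As written, a device-related tongue lesion could lead to dismissal, dismissal could end the required follow-up, and the lesion's outcome could go unrecorded. This assumes that *dismissed* means *terminated*.

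At most 8 children could be affected, with 0 contacts required after dismissal. The documents give no lesion rate in children, and a rate of zero is compatible with them, so none is assumed here.

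Two stronger readings are tempting and should be resisted. One is that the event itself would go unreported; the 10-day report and the assessment of relationship to the device still apply, so only the outcome is exposed. The other is that the protocol forbids further follow-up; it only allows it to stop.

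**What to change.** In ADVERSE EVENTS, keep the first two end points and replace the third with:

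> Device-related adverse events open at dismissal, withdrawal or the end of Session 5 will be followed, by telephone if needed, until resolved or judged chronic or stable, unless the family declines further contact; the outcome will be recorded.

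Then check that the consent and assent wording agrees. The sentence covers the dismissal and withdrawal routes, and it removes the doubt over whether *terminated* includes normal completion.

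The cost is one amended sentence, a check of the forms, and one outcome field per open event. The downside is a small amount of contact and record-keeping after participation ends, for at most 8 children. No endpoint, sample size or analysis changes.

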- 4) The BrainPort already has CE Mark approval and pending FDA approval (final safety study documents submitted to the FDA August 2013), and should be available for purchase by 2014, at least in Europe and Canada. Whether the device could be useful in a pediatric population is an important clinical question.
- 5) The relation of the anticipated benefit to the risk presented by the study is at least as favorable to the subjects as that provided by available alternative approaches (blind training).

RESEARCH DESIGN AND METHODS

Primary Efficacy Endpoints

The primary efficacy endpoint for this study is a statistical analysis of subjects' improvement over baseline in any of the following areas: light detection, light localization, movement perception, and standardized object recognition tasks after use of the BrainPort. To test our primary endpoints, we will use a within-subjects repeated measures design.

Statistical analysis (general)

All data will be stored in a password encrypted PASS Statistics version 18 database whose contents will be available only to members of the study team. We will use t-tests to assess the differences in performance for all measures on our assessment battery, pre- and post-training. Bonferoni correction will be used to correct for experiment-wise error rate (*i.e.*, the increased possibility of finding many significant correlations due to the multiple tests conducted). Separate analyses of covariance will be performed using age, sex, education, and years since diagnosis as covariates. The major advantage of this design is subject homogeneity; that is, random subject effects are reduced. Because the subjects serve as their own controls, factors such as age, education, mental status, motivation, and disease are completely matched; thus these factors will not contribute to the main effect of training. Matching is always very difficult in individuals with eye disease, and this design resolves this confound.

Subject selection criteria

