- 5. Known allergies to nickel, gold or other components of stainless steel.

Study Duration

The duration will be up to 5 visits over the course of approximately 2 weeks. Study sessions will be limited to 90 minutes in length. A subject can elect to have up to two sessions per day which would reduce the duration of the study. We are requiring that at least one parent or caregiver be present for all study visits.

Study Procedures

Screening and Enrollment

The study will be explained to the potential candidates and their parents, including the purpose, procedures, expectations for participation, benefits, and risks. Upon request, an IRB approved patient information sheet explaining the study can be provided for review at home. If the potential subject shows interest in the study, additional pre-screening questionnaires will be administered to determine eligibility. Specifically, our study coordinator will review the inclusion and exclusion criteria over the telephone. We have included this paradigm successfully in other studies with the Brainport, which reduces the likelihood that a subject will travel to our site at their own expense but not meet our inclusion and exclusion criteria.

If the potential subject has successfully passed our pre-screen tests over the phone, then he or she will be provided by mail with the Informed Consent form and the HIPAA Research Authorization Form, the participant Assent form and the Parental Permission form, which will have been approved by the University of Pittsburgh Institutional Review Board. We will offer to provide a JAWS compatible version and/or an audio version to the subject prior to their arrival so that they can review it at their own pace and with their families. These same documents will be reviewed again with the subject and their family member upon arrival for the initial visit. In the event that the subject is not able to sign their own name, a proxy designated by the subject may provide the signature.

A HIPAA research authorization will allow the researchers to access the subject's medical records related to their diagnoses and to enable further disclosure of the subject's study data to the study personnel, study monitor, clinical research organization, and the IRB.

Overview of Study Design

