Potential subjects will be examined to verify that vision in each eye is light perception or worse by the PI according to standard practices at the UPMC Eye Center. Subjects will not need to be dilated. In most cases, our blind subjects have prosthetic eyes or have such badly damaged eyes that verification of blindness by clinical exam does not need to occur. In these instances, the ocular examination will be waived. Inspection of the oral cavity, medical and medication history will be performed.

Psychophysical assessments: We begin with rudimentary vision assessment such as light perception and proceed to increasingly complex visual tasks which approach "normal" vision as the device allows. In the event that a subject is not able to perceive better than light perception, tests which ascertain higher functions will not be administered. Below is a representative description of the tests that we commonly employ with BrainPort studies.

The Basic Assessment of Light Motion (BaLM) and Basic Assessment of Grating Acuity (BaGA) have been developed with the intent of testing artificial vision devices, which provide the most rudimentary visual precepts. They have been used to quantify such qualities as light detection, temporal resolution and light motion as well as "grating acuity" for situations where standard resolution acuity is nonexistent. The methods for testing have been described in Artificial Vision by Mark Humayan. Both tests run on a software platform and are presented on a computer LCD screen to the subject. The stimuli they present consist mainly of large targets of varying patterns. The subject is seated in a regular chair while looking at a computer display for these non-invasive tests, each of which last an average of 10 minutes or less. The subject is able to stop the test in the event they feel they need to get up and move around. All visual acuity measurements will be performed by a single examiner. For baseline testing, while one eye is tested, the other will be occluded. We use this to make sure that both eyes have visual acuity of LP or worse to meet entry criteria. Subsequent testing using the Brainport is done using the camera pointed at the computer screen. All vision tests will be performed in a room with standardized illumination.

BaLM Test

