Device labels and labeling have developed for the proposed study. The device package label and all device manuals will include the statement "Caution: Investigational Device. This device is limited by Federal law to investigational use". Wicab, Inc., the manufacturer of the BrainPort provides all investigators with detailed instructions for use of the device, which include indications, warnings, precautions, use instructions, and potential adverse events.

Training Curriculum

A BrainPort training program has been developed based upon the preliminary experiences and is summarized below. We have found that subjects do not all learn at the same pace, so some subjects may advance to the next level while others need additional time to master certain skills. The skills attained will be documented in the subject case report form. This will be monitored to ensure that the pace of training is appropriate. As mentioned, return subjects who have already completed our training program and who know how to use the device will undergo a shortened, refresher as opposed to going through the entire curriculum.

Basic BrainPort Skills

Subjects will be instructed on how to wear and operate the BrainPort device. The use of controls, such as zoom and preset gain settings, on/off switches, contrast inversion will be practiced. Handling, maintenance and care of the device, as well as troubleshooting and battery replacement will be covered. Once this is mastered, the first task involves a white felt line stimulus on a black felt background. Subjects are encouraged to explore how to point the camera at the stimulus, using their hands for biofeedback. The line is then placed in various positions on the felt background (up, down, left, right) and in various orientations. More difficult tasks include finding the stimulus on a white board or blackboard without the benefit of tactile assistance.

Head movement skills and spatial relationships

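### Does the shortened refresher for already-trained returning subjects bias the pre/post comparison, given that the plan has no rule on prior BrainPort use?

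*Combined protocol and SAP*

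**What the plan says.** Under Training Curriculum, the combined protocol and SAP states that "return subjects who have already completed our training program and who know how to use the device will undergo a shortened, refresher" rather than the full programme. The sentence opens as if repeating an earlier statement, but no earlier section mentions returning subjects or a refresher.

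Places that bear on whether such a child could enrol:

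- Subject selection criteria: 8 blind children aged 7 to 18 are to be recruited, and one source is "the established volunteer list of over 200 blind subjects from the Sensory Substitution Laboratory".
- Overview of Study Design: "Our lab has trained over 100 subjects to use the BrainPort device". No ages are given.
- Inclusion and Exclusion Criteria: the items touching on the device or its training ask for willingness to use it and ability to complete the training period. Prior use is neither allowed nor barred.
- Study Duration: "The duration will be up to 5 visits over the course of approximately 2 weeks". A shorter training course fits within this limit.

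Places that bear on measurement and analysis:

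- The visit schedule lists for Session 5: "Repeat outcomes assessments with Brainport".
- Evaluation Procedures/Outcomes Assessments has baseline screen tests done one eye at a time, and then: "Subsequent testing using the Brainport is done using the camera pointed at the computer screen".
- Overview of Study Design makes retesting wait until training is complete and "the subject has demonstrated basic proficiency with the device".
- Statistical analysis (general): "Separate analyses of covariance will be performed using age, sex, education, and years since diagnosis as covariates". The subgroup lists under both Analysis of Test Results headings cover type of blindness, age, gender and TBI. Neither list includes prior use.

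**The concern.** The plan describes a different training course for people already trained, but no other section deals with them. Recruitment draws on the laboratory's own volunteers, so there is a route on paper for a returning child to be one of the 8.

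The within-subject design would not remove the effect of earlier training. A child serves as his or her own control only for factors that act equally at both time points. Retained device skill acts at Session 5, when the device is worn, and not at a baseline taken without it. That baseline is explicit for the screen tests and inferred for object recognition. If the change is read as the gain produced by this study's training, a returning child would overstate it, and no planned covariate or subgroup would show this. With only 8 children, one unusual observation carries weight.

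**Working it through.** **Is there an affected child?** The bias needs a child aged 7 to 18 who has already completed this laboratory's programme. The introduction reports results in adults and presents the pediatric question as open. The volunteer list and the count of trained subjects carry no ages. The number of returning children may therefore be zero.

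**Which contrast is tested?** The wording points both ways:

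| Section | Contrast suggested |
|---|---|
| Primary Efficacy Endpoints | improvement following use of the device |
| Subject selection criteria (power statement) | naive condition against BrainPort condition |
| Visit schedule, Session 5 | assessment with the device |
| Analysis of Test Results (both) | before against after device use |
| Statistical analysis (general) | before against after training |

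Four of the five fit device against no device. On that contrast a returning child's gain is a real device effect, and only generalisability to device-naive children is affected. The fifth keeps the training reading open.

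**How large could it be on the training reading?** The plan's own figure (n = 8, p < 0.05, power above 0.8) cannot be reproduced because no effect size or SD is stated. Solving backwards for a paired t-test (noncentral t, 7 degrees of freedom), 80% power at n = 8 needs a mean change of 1.156 SD two-sided, or 0.978 SD one-sided. Sidedness is not stated; two-sided is used below.

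Assumptions, since the documents give neither value: m of the 8 children are returning subjects, each with x SD of extra gain, and the within-group SD is 1.

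- Shift in mean = m·x/8
- Root of the expected sample variance = √(1 + m(8 − m)x²/56)

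For m = 1, x = 1: shift = 1/8 = 0.125. SD = √(1 + 7/56) = √1.125 = 1.061. Standardized effect = (1.156 + 0.125)/1.061 = 1.21.

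Simulated probability of p < 0.05 (1,000,000 replicates per row) for three values of the naive children's true gain:

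| Returning children | Shift (SD) | Shift / 1.156 | Gain 0 | Gain 0.5 | Gain 1.156 |
|---|---|---|---|---|---|
| none | 0 | 0% | 0.050 | 0.232 | 0.800 |
| one, x = 0.5 | 0.0625 | 5% | 0.050 | 0.271 | 0.831 |
| one, x = 1 | 0.125 | 11% | 0.049 | 0.295 | 0.843 |
| one, x = 1.5 | 0.1875 | 16% | 0.048 | 0.301 | 0.842 |

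One returning child does not raise the false-positive rate, because the same outlying value that lifts the mean also widens the SD. At 0.0125 (a Bonferroni level if there is one test for each of four areas, an assumption) the simulated rates are 0.0127 with no returning child and 0.0125, 0.0120 and 0.0115 for the three rows with one.

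**What limits x?** Naive children are retested only after reaching basic proficiency, and the curriculum moves on as each skill is mastered. This is a floor and does not guarantee equal skill, but it narrows the gap. If it closes the gap, x = 0 and nothing shifts.

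**Would covariates or subgroups help?** With 8 children and perhaps one returning, neither could usefully estimate an effect of prior use. Their silence costs nothing.

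**The case for a change.** The strongest contrary case is that the refresher sentence is operative text and that settling the policy beforehand is cheap. If a returning child took one of the 8 places and was later set aside, power at the 1.156 SD effect would fall from 0.80 to 0.72 with 7 children, and the exclusion would be decided after the fact. Two returning children at x = 1 would shift the mean by 2/8 = 0.25 SD and raise the false-positive rate to about 7%.

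The silence is real, and an explicit sentence would be tidier. The arithmetic is also right on its assumptions. But nothing in the documents suggests one trained child in this age range, let alone two. The 7% figure further requires that naive children gain exactly nothing while returning children gain a full SD, which sits badly with the proficiency requirement. On the device reading, such a rejection would not be an error at all.

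A returning child would also be hard to miss. The refresher cannot be given without knowing who has been trained before, and the case report form already documents the skills each child attains. No section says that it records prior training, but with 8 children an analyst can mark one individual in a listing and look at the result without that child.

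**Conclusion.** No change to the plan is called for. The gap is missing detail, and the sentence behind it may be carried over from other laboratory text, since its back-reference has no antecedent. The documents do not show that following the plan as written gives a wrong answer. Excluding prior users, or admitting and identifying them, would each be defensible, so this is a policy choice for the sponsor and not the correction of an error.

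The effect is zero if no trained child enrols. With one such child it is an illustrative 0.06 to 0.19 SD shift in the mean, with the false-positive rate still at about 5%. This rests on assumed values for the number of returning children and their extra gain, on a two-sided paired t-test, and on reading the change as a training effect. Evidence that several trained children of this age were likely to enrol would alter the conclusion; the documents contain none.
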